14. STATISTICAL CONSIDERATIONS

14.1. STATISTICAL ANALYSIS

A full statistical analysis plan (SAP) will be in place prior to any comparative analyses according to guidelines (38). All analyses and patient populations will be predefined in the SAP. Both intention to treat (ITT) and per protocol (PP) analyses have biases so neither are taken as a 'gold standard' for non-inferiority trials but can make critical differences to the results of a trial (39). The ITT population includes all randomised patients. The PP population includes all patients who received their randomised intervention. At the time of the final analysis, KARDS will be analysed and reported according to CONSORT extension for Non-Inferiority and Equivalence Randomized Trials (40). Trial outcomes will be analysed primarily for the PP population and repeated, for sensitivity reasons, for the ITT population. KARDS protocol v1.0_190927

ANALYSES OF THE PRIMARY OUTCOME MEASURE

Adjusted estimates of the treatment effect will be estimated from multivariable regression modelling of the KOOS pain score at 12 months. Statistical significance of non-inferiority of KJD relative to KR will be based on a 2-sided likelihood-based test with a type 1 error of 2.5% in both tails, assuming KOOS pain scores (or transformed scores if appropriate) are normally distributed and adjusted by baseline score at the time of randomisation and stratification factors (delivery unit and OA severity). If the 95% confidence interval for the absolute difference in means between KJD and KR lies entirely below or includes the non-inferiority boundary (see Section 14.2) then there would be insufficient evidence to reject the null hypothesis that KJD is inferior to KR. Conversely, if the 95% confidence interval lies entirely above the non-inferiority boundary then there would be evidence to reject the null hypothesis and conclude KJD is non-inferior to KR. Further modelling will include confounders of age and BMI, observing and addressing non-linearity through use of fractional polynomial transformation. Secondary analyses of the primary outcome measure will be considered. If non-inferiority is demonstrated and KJD appears superior to the KR, based on estimated effect and CI, statistical significance for superiority will be calculated based on an ITT analysis with similar modelling strategy. A secondary analysis of the primary outcome measure will be based on random effects multilevel modelling to account for the nested and longitudinal structure of the data over the full 24 months follow-up.

ANALYSES OF SECONDARY OUTCOME MEASURES

Analysis of PROMs (KOOS components, OKS, Pain VAS and EQ5D-3L) will focus on reporting the pre-specified dimensions of the individual questionnaires. Questionnaire responses will be combined and transformed into dimension scores, according to scoring manuals where these exist, presented graphically and longitudinally. Standardised area under the curve statistics will be compared across treatment groups as an analysis conditional on patient survival.

Range of motion and timed up and go functional assessments will be reported descriptively.

The number of complications, specifically infection, will be reported as unique events and unique patients experiencing events. Joint survival is defined as time from surgery to date of additional secondary procedure, specifically knee replacement/revision knee replacement, or date of censor at patient last follow-up. Joint survival will be estimated using the method of Kaplan and Meier and presented graphically with 12 and 24 month survival estimates and risk (hazard ratio) of additional treatment in KJD as compared to KR, in the ITT population. Global quality of life (QoL) collected as part of the EQ5D-3L may be used in a quality adjusted analysis to analyse QoL and time to secondary procedure simultaneously. Radiographic assessment of joint space width, as an indicator of intrinsic cartilage repair, over a two-year period will be reported descriptively in the KJD group.

EXPLORATORY ANALYSES

Planned exploratory descriptive subgroup analyses will be carried out by delivery unit, type of KR (partial/total), type of pin (hydroxyapatite coated/not) and baseline functioning (poor/better). Tests of heterogeneity of treatment effects across subgroups (not treatment effects within subgroups) may be appropriate.

MISSING DATA

Missing outcome data may be imputed dependent on level of missing-ness and reasons for missing-ness assessing the assumption of missing at random. Sensitivity analyses will report under different assumptions about the missing data. The impact of surgical experience is expected to be minimal; however, sensitivity analyses may be conducted to investigate any impact of surgeon experience on estimates of treatment effect (41).

INTERIM ANALYSES

Interim analyses will be conducted on an annual basis for presentation to the DMEC who will monitor primarily safety outcomes and data quality as well as the underlying assumptions of the statistical design (specifically variability on the primary outcome measure). The DMEC will also review key baseline characteristics (e.g. pain) and stratification factors to ensure balance. Analyses will be agreed and documented upfront by the independent DMEC members. No formal guidelines for stopping the trial early are in place since no formal planned interim analysis of the primary outcome measure is planned (precluded by the follow-up and recruitment timelines).

KARDS protocol v1.0_190927

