11.2. SECONDARY OUTCOME MEASURES

1. Patient reported outcomes and quality of life outcomes

a) KOOS (At component level)

KOOS domains (except pain): other Symptoms, Function in daily living (ADL), Function in sport and recreation (Sport/Rec) and knee related Quality of life (QOL).

b) Pain VAS

The pain VAS is a unidimensional measure of pain intensity (26,27), which has been widely used in diverse adult populations, including those with rheumatic diseases (26,28–30). The pain VAS is a continuous scale comprised of a 10cm horizontal length ranging from "no pain" (score of 0) to "pain as bad as it could be" or "worst imaginable pain" (score 100 [100mm scale])

c) Oxford Knee Score (OKS)

OKS is a short, reproducible, valid PROM consisting of 12 items which provides an overall scale for assessing outcomes of knee interventions and is sensitive to clinically important changes (31–33). Each question is scored from 0 to 4 with 4 being the best outcome. This method when summed produces overall scores from 0 to 48 which reflects the severity of problems that the respondent has with their knee, with 48 being the best outcome (i.e. least symptoms). It takes approximately

5 minutes to complete the form. Whilst the applicability of the OKS to the general OA population is unclear, it is commonly used for joint replacement registries and is the outcome measure of choice of the National Joint Registry for England, Wales, Northern Ireland and the Isle of Man.

2. Objective assessment of knee function

- a) The active range of movement. Measured using a goniometer at 3, 12 and 24 months, the angles in degrees will be measured with the affected leg fully extended (extension) and fully bent (flexion), to determine the range of movement (i.e. the difference in angles between the two values, extension minus flexion). A flexion deformity will be measured as a positive value and hyperextension will be recorded as negative value.
- b) **Timed-up-and-go test**. Time in seconds for the participant to rise from a chair, walk three meters, turn around, walk back to the chair, and sit down.

3. Incidence of complications

Intra-operative complications: Complications occurring during the initial trial operative procedure will be recorded.

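### The per-protocol-first rule in Section 14.1 reaches complications, so a patient switched from, or probably abandoned during, the allocated procedure leaves the lead harms table

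*Protocol*

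**What the plan says.** Protocol Section 14.1 defines two populations. For ITT: "The ITT population includes all randomised patients". For PP: "The PP population includes all patients who received their randomised intervention". It then gives a general rule: "Trial outcomes will be analysed primarily for the PP population and repeated, for sensitivity reasons, for the ITT population".

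Section 11.2 lists "3. Incidence of complications" as a secondary outcome. Intra-operative events belong to it: "Complications occurring during the initial trial operative procedure will be recorded" Unplanned further surgery on the knee is placed under the same outcome.

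The analysis text for complications in Section 14.1 is one sentence, and it names no population: "The number of complications, specifically infection, will be reported as unique events and unique patients experiencing events".

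Elsewhere, Section 14.1 says so when it departs from the default. Joint survival is to give the "risk (hazard ratio) of additional treatment in KJD as compared to KR, in the ITT population". If non-inferiority is shown and KJD looks better, "statistical significance for superiority will be calculated based on an ITT analysis with similar modelling strategy". The protocol contains no such exception for complications and defines no safety or as-treated set.

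**The concern.** A lead analysis of harms should not let the harm decide who is counted. Here it can. If an intra-operative event stops the allocated procedure, the patient has arguably not received it. That patient then leaves the PP set, and the event goes with them. A patient given the other procedure is outside PP on any reading.

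Section 14.1 justifies considering PP by pointing out that both populations carry bias in non-inferiority trials. That argument concerns the non-inferiority conclusion on pain. It gives no reason to put PP first for a descriptive count of complications.

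What is at stake is the headline complication and infection figure for a procedure that, according to Section 5.1, has not been studied in the NHS. The primary analysis and the sample size are not affected.

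**Working it through.** **1. Does the rule cover complications?**

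| Item in the protocol | Population stated |
|---|---|
| Trial outcomes in general (14.1) | PP first, ITT as sensitivity |
| Superiority test on the primary outcome (14.1) | ITT |
| Joint survival: knee replacement or revision (14.1) | ITT |
| Complications, including infection (14.1, 11.2) | none, so the default applies |
| Other unplanned surgery on the knee (11.2) | none, so the default applies |

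**2. Who leaves the lead table?**

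| Patient | In PP? | Where the ITT repeat counts the complication |
|---|---|---|
| Allocated procedure completed; frame or pins fail later | Yes | Randomised arm |
| Allocated procedure started, then abandoned | Ordinarily no, but *received* is undefined | Randomised arm, which is also the procedure started |
| Given the other procedure from the outset | No | Randomised arm, which is not the procedure they had |
| Complication after randomisation, never operated on (13.2.2 collects from randomisation) | No | Randomised arm |

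**3. What size could this have?** The only input from the protocol is the arm size of 172 in Section 14.2: 146 / (1 − 0.15) = 171.8, rounded up to 172, which agrees with the plan. Everything else below is assumed.

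Let f be the share of KJD patients outside PP, q_f their complication risk, and q the risk in the remaining patients. Then

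- PP rate = q
- ITT rate = (1 − f)q + f·q_f
- ITT − PP = f(q_f − q)

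With f from 2% to 10%, q_f from 50% to 100% and q from 20% to 40%:

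- smallest gap: 0.02 × (0.50 − 0.40) = 0.002, or 0.2 percentage points
- largest gap: 0.10 × (1.00 − 0.20) = 0.08, or 8 percentage points
- patients outside PP: 172 × 0.02 = 3.4 to 172 × 0.10 = 17.2

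A count version of the extreme case, in which every abandonment carries a serious complication, takes 10 such complications after completed frames plus a = 3, 5 or 8 abandoned attempts:

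| a | PP: 10/(172 − a) | ITT: (10 + a)/172 | Gap (percentage points) |
|---|---|---|---|
| 3 | 10/169 = 5.9% | 13/172 = 7.6% | 1.6 |
| 5 | 10/167 = 6.0% | 15/172 = 8.7% | 2.7 |
| 8 | 10/164 = 6.1% | 18/172 = 10.5% | 4.4 |

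(Gaps are taken before rounding.)

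**4. Can the sign reverse?** Yes, whenever q_f is below q. Take 17 KJD patients with an event and 10 event-free patients switched before surgery. PP is 17/162 = 10.5% and ITT is 17/172 = 9.9%, so PP makes KJD look slightly worse.

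**The case against.** The strongest reply is that the planned ITT repeat already supplies the fuller figure. In the table above, (10 + a)/172 is the ITT rate: an abandoned KJD stays under KJD there, whatever follows. Safety oversight is also independent of PP. Complications are collected from randomisation (13.2.2, 13.2.3), the DMEC sees data by randomised group (20.2.3), and the REC receives annual safety reports (13.2.2, 13.3). The complications analysis is a count with no test attached. All of this stands, and it limits the point to which table leads.

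It also rules out some stronger readings that a reader might infer:

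- *Harms from failed KJD attempts are hidden.* They are not; they appear in the ITT repeat.
- *Neither planned set counts harms by the procedure started.* For an abandoned attempt, ITT does. The statement holds only for patients given the other procedure from the outset.
- *The bias must favour KJD.* No abandonment rate is given for either arm. Section 8.2 requires external fixation experience or a limb reconstruction fellowship, plus trial training, and Section 14.2 calls external fixation common. Step 4 shows that the sign can reverse.
- *A large fraction of the true rate is missed.* Any such figure rests on assumed counts in which every abandonment carries a serious complication.

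A second reply is that Section 14.1 leaves the populations to the SAP, which is not at hand. That would answer a complaint about missing detail. It does not answer this one, because the protocol states a PP-first rule that includes complications. A SAP that led with another set for harms would depart from that rule.

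A third reply is that *received* might be read to include a started frame. That is possible, since the word is undefined. A switched patient is outside PP either way.

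**Conclusion.** The point holds in a limited form. Taken literally, Section 14.1 makes PP the lead population for complications, infection and unplanned further surgery other than replacement or revision. It therefore allows a complication to remove its own patient from the lead table. For switched patients this follows directly from the text. For abandoned procedures it rests on the ordinary meaning of an undefined word.

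The size is unknown. The range of 0.2 to 8 percentage points is illustrative and assumes that patients outside PP have the higher risk; without that assumption the sign is open. No data are lost, and the conclusion on pain is untouched. The change is still worth making, because it removes an outcome-dependent exclusion from the headline harms figure at little cost.

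**What to change.** In Section 14.1, and in the SAP to match:

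- Exempt complications, infection and unplanned further surgery from the PP-first rule.
- Report them primarily for all participants in whom a trial procedure was started, grouped by the procedure first started. An abandoned KJD then stays under KJD whatever follows.
- Place the randomised-arm (ITT) table alongside. It also holds any complication in a patient who was never operated on.
- Leave joint survival in ITT, as stated.
- Define *received* for PP membership, saying explicitly how a procedure that was started and abandoned is classified.

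The cost is a wording change and one extra table. The surgical CRF described in Section 11.2 already records whether the mandatory components were performed and explains deviations, so no new data are expected to be needed. The reported complication rate may be slightly less favourable. Sample size and the primary analysis do not change.

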8.2.1. Delivery units

To facilitate the hybrid expertise based design, surgeons are categorised into delivery units. There are two categories of delivery unit based on the interventions the surgeon is authorised to carry out within the trial:

- Single delivery unit: Consists surgeons who are authorised to deliver one type of surgery (KJD or KR)
- Dual delivery unit: Consists surgeons who are authorised to deliver both types of surgery (KJD and KR)

A centre is eligible to participate if they have at least one complete delivery unit. A delivery unit is defined as 'complete' in the following ways:

Single delivery unit: At least one surgeon authorised to deliver only KJD and at least one surgeon authorised to deliver only KR

• Dual delivery unit: At least one surgeon authorised to deliver both KJD and KR.

A mix of delivery units within a centre is acceptable, however movement of surgeons across delivery units is not permitted during the trial.

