10.3. SURGERY

Surgical consent will be reconfirmed on the day of surgery and participants will be assessed by the clinical team (anaesthetist, and surgeon and/or their assistant) as per standard of care prior to proceeding with surgery.

In the case of single delivery units, patients will be operated on by a surgeon authorised to deliver one type of surgery (KJD or KR as relevant). In the case of dual delivery units, patients will be operated on by the intended surgeon regardless of their randomised allocation.

A surgical manual will be provided detailing the surgical procedures for both interventions and highlighting mandatory components.

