14.2. SAMPLE SIZE

Sample size and power calculations are based on a non-inferiority hypothesis for the primary outcome measure. Secondary outcome measures are not powered. The statistical design is based on a distribution-based method informed by data from the previous trial (16), clinical co-applicant experience and consensus, reported recommendations of minimally important differences in knee disease and feedback from the PPI focus group. A median 12-point credible minimal difference (range 4 to 20) for patient reported KOOS pain has been recommended (19) and 13-points for patients with knee OA (42). This is supported by patients who report they would accept a 10-15% (translated to 10-15 points) increase in pain to retain their knee. Based on this consensus for a minimally important difference, the non-inferiority threshold is defined to be at least 33% less at a threshold of 8. Previous observational studies of KOOS pain have reported variability (SD) from 15 to 21 (3,43–45).

A one-sided significance of 2.5% is used which allows two-sided 95% confidence intervals to be presented. The target recruitment is based on demonstrating non-inferiority within a limit of 8 points. Ignoring drop-out within 12-months, 146 patients recruited to each group would have 90% power to demonstrate non-inferiority within a threshold of 8 points and variability assumed SD=21. Allowing for 15% dropout, the target is inflated to 172 patients in each group resulting in an overall recruitment target of 344 patients. The underlying assumptions of the statistical design will be monitored by the DMEC.

No sample size adjustment has been made to accommodate surgeon learning curve since external fixation is a common procedure which orthopaedic surgeons are frequently required to do for trauma.

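### In single delivery units surgeon is nested in arm, but neither the primary 12-month model nor the 90% power allows for variation between surgeons

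*Protocol*

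**What the plan says.** Section 8.2.1 calls a single delivery unit complete when it has the following: "At least one surgeon authorised to deliver only KJD and at least one surgeon authorised to deliver only KR". Surgeons may not change units during the trial. Section 10.3 confirms that in single units the operating surgeon is authorised for one procedure only, whereas in dual units the intended surgeon operates whatever the allocation. Section 9.4 explains that the design exists because only some surgeons have KJD experience and some may lack individual equipoise.

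For the primary outcome, section 14.1 says: "Adjusted estimates of the treatment effect will be estimated from multivariable regression modelling of the KOOS pain score at 12 months". The stated adjustments are baseline score, delivery unit and OA severity, and the 95% interval from this model decides non-inferiority. Clustering appears only later in the same section: "A secondary analysis of the primary outcome measure will be based on random effects multilevel modelling to account for the nested and longitudinal structure". That analysis covers the full 24 months. A sensitivity analysis on surgeon experience is optional.

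Section 14.2 gives the power: "146 patients recruited to each group would have 90% power to demonstrate non-inferiority within a threshold of 8 points and variability assumed SD=21". It mentions surgeons only to decline an adjustment for the learning curve, which is a different matter from clustering.

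**The concern.** In a dual unit the same surgeon treats both arms, so a surgeon's general level of results largely cancels from the comparison. In a single unit it does not. If one unit's KJD surgeon gets somewhat better or worse results than its KR surgeon for reasons unrelated to the procedure, that gap is part of the unit's estimated treatment difference. A delivery-unit term removes differences between units, but the two surgeons sit inside the same unit.

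A regression that treats patients as independent given unit, baseline and severity leaves this component out of the standard error. In a non-inferiority trial the error is in the unsafe direction: a narrower interval clears the margin of -8 more easily. What is at stake is the one-sided 2.5% error rate of the trial's main conclusion and, to a lesser degree, the power quoted for it.

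**Working it through.** **Inputs from the protocol.** One-sided 2.5%, margin 8, SD 21, 146 evaluable per arm, 15% dropout, 172 per arm and 344 in total (14.2); 1:1 allocation (9.4). The true difference is not stated. Zero is assumed because it reproduces the plan.

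**The plan's own figure.**
- n = 2 × 21² × (1.960 + 1.282)² / 8² = 145 per arm.
- At 146 per arm the standard error is 21 × √(2/146) = 2.458.
- Power = Φ(8/2.458 − 1.96) = 0.902, or 0.900 with the t distribution.
- 146/0.85 = 171.8, so 172 per arm and 344 in total.

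The figures reproduce, with a design effect of 1. There is no arithmetic error.

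**Assumptions not in the protocol.** The surgeon ICC is varied over 0.01 to 0.10. The number of clusters uses the 16 sites targeted for the end of the pilot (7.2) as a proxy. The base layout is all single units, with one surgeon per arm in each, so m = 146/16 = 9.125 evaluable patients per surgeon.

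**Formulas.**
- Design effect: DE = 1 + (m − 1) × ICC.
- Factor by which a valid interval is wider: √DE.
- One-sided error of a model that ignores surgeon: 1 − Φ(1.96/√DE).
- Power of an analysis that allows for surgeon: Φ(8/(2.458 × √DE) − 1.96).

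| ICC | DE | Valid CI wider by | One-sided error (formula) | One-sided error (simulated) | Power |
|---|---|---|---|---|---|
| 0.01 | 1.081 | 4% | 3.0% | 2.8% | 88% |
| 0.02 | 1.163 | 8% | 3.5% | 3.6% | 85.5% |
| 0.05 | 1.406 | 19% | 4.9% | 4.9% | 78% |
| 0.10 | 1.812 | 35% | 7.3% | 7.4% | 68% |

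The simulation used 20,000 runs, 16 single units, 9 patients per surgeon, unit as a fixed effect and a true difference of −8. With an ICC of zero it returned 2.6%. The power column uses a normal critical value. With only 16 unit-level differences the reference would be t on about 15 degrees of freedom, which lowers power further.

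**Milder layouts.**
- Two surgeons per arm in each of 16 single units: m = 146/32 = 4.56. At ICC 0.02 and 0.05, DE is 1.071 and 1.178, error 2.9% and 3.6%, and power 88% and 85%.
- Half the units dual, and these assumed to add no variance: DE = 1 + 0.5 × 8.125 × ICC, which is 1.081, 1.203 and 1.406 at ICC 0.02, 0.05 and 0.10. The formula gives errors of 3.0, 3.7 and 4.9%; a simulation of 4,000 runs gave 2.9, 4.1 and 5.7%. Power is 88% at ICC 0.02 and 84% at 0.05.

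**Offsets to power (base layout).** With baseline correlation ρ, replace DE by DE − ρ² in the variance.
- SD 21 and an assumed ρ of 0.4: power 90% at ICC 0.02 and 83% at ICC 0.05.
- SD 18 with no baseline credit: power 94% at ICC 0.02 and 89% at ICC 0.05.

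Neither offset repairs the interval. The error depends on the ratio of true to assumed variance. A smaller SD leaves that ratio unchanged. If baseline explains only patient-level variance, the ratio at ICC 0.02 rises slightly, from 1.163 to (1.163 − 0.16)/(1 − 0.16) = 1.194.

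**The case against.** The strongest reply is that the harm is conditional. Surgeon ICC, number of surgeons and share of single units are all absent from the protocol, and the base layout is unfavourable. Sixteen is a pilot target, 8.2.1 sets a minimum of one surgeon per procedure rather than exactly one, and units may be mixed within a centre. More surgeons or more dual units bring the error close to nominal at a small ICC. This stands, and it is why the result is a range.

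On power, section 14.2 says "Previous observational studies of KOOS pain have reported variability (SD) from 15 to 21" and the plan takes the top of that range. It also takes no credit for baseline adjustment, and the DMEC reviews the design assumptions. This stands too. A reader might infer that the trial certainly falls short of 90% power; the document does not support that. Nor does it show as fact that the interval is too narrow, since that requires an ICC above zero.

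A third reply is that 14.1 does not literally state independent errors and that the variance structure belongs in the SAP, which is not shown. This stands only in part. A SAP could add the term. But the protocol names its nested structure and assigns random effects to a secondary 24-month analysis, while the decisive 12-month model lists its adjustments without surgeon. The sample size, with its implicit design effect of 1, is fixed in the protocol.

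Finally, keeping 344 recovers no lost power. That is true. The change corrects the error rate and makes the power statement accurate.

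**Conclusion.** The concern holds in conditional form and should be fixed. In single units the surgeon component enters the treatment contrast, the delivery-unit term cannot absorb it, and the primary model as stated has nothing else that would. Any positive surgeon ICC therefore makes the decisive interval too narrow, in the direction that favours declaring non-inferiority.

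The size cannot be fixed from the document. In the base layout, one-sided error runs from about 3.0% at ICC 0.01 to 7.3% at ICC 0.10. With two surgeons per arm it is about 2.9% and 3.6% at ICC 0.02 and 0.05. With half the units dual it is about 3%, 4% and 5 to 6% at ICC 0.02, 0.05 and 0.10. Power may still be near 90% at a small ICC because of the conservative SD and the baseline adjustment, but those features do not restore the error rate. A reader might also infer that 146 or 344 was miscalculated. It was not: both reproduce for independent patients.

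**What to change.** In 14.1, add a random operating-surgeon effect to the primary 12-month model, with surgeon-by-treatment variation in dual units, or use an equivalent cluster-adjusted variance. Apply a small-sample degrees-of-freedom correction such as Kenward-Roger. Keep baseline score, delivery unit and OA severity as adjustments.

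In 14.2, state the assumed surgeon ICC and cluster size and give the power as conditional on them, or justify an ICC of zero. Keep the target of 344.

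Cost: a wider interval, about 4 to 19% at ICC 0.01 to 0.05 if all units are single with one surgeon per arm, and less otherwise; a possibly less favourable stated power; and identification of the operating surgeon on the surgical CRF that section 11.2 already provides for. No extra patients are needed. The wording should be settled before any comparative analysis.

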6.2. SECONDARY OBJECTIVES

To examine and report:

- 1) Patient reported outcomes and quality of life within 24 months after surgery
- 2) Objective assessment of knee function
- 3) Rates of complications, including infection
- 4) The need for further intervention within 24 months after surgery
- 5) KJD's potential as a cartilage regenerative therapy
- 6) Estimate of short and long term cost-effectiveness
- 7) Implementation processes and intervention fidelity
- 8) Participant experiences of the trial/interventions and possible facilitators or barriers to wider implementation

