9.4.1. Timing of randomisation

Randomisation should take place on the same day as the baseline visit, which can be up to 6 weeks before the planned date of surgery. The range of movement and timed up and go tests should be performed and all baseline questionnaires completed BEFORE the participant is randomised (see Section 12 for further details of baseline assessments).

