12.2. SCHEDULE OF CLINICAL ASSESSMENTS / DATA COLLECTION POINTS

TRIAL VISIT	1	2	3	4	5	6	7	8
Time from date of surgery	≤6 weeks before	0	Up to Day 7	Week 6	Month 3	Month 6	Month 12	Month 24
Time window	-	-	-	-	+/- 4 weeks	- 2 weeks + 6 weeks	+/- 6 weeks	+/- 8 weeks
Visit type	Baseline	Surgery	Post- operative	Fixator removal	Follow up (clinic)	Follow up (post / online)	Follow up (clinic)	Follow up (clinic)
Treatment group	All	All	All	KJD only	All	All	All	All
				Unity				
Confirmation of eligibility	Х							
Informed Consent	Х							
Patient demographics	Х							
Medical history	Х							
OA severity (Kellgren- Lawrence grade based on standard AP and lateral x-rays)	x							
Physical examination of knee	X°							
Range of movement using goniometer	х				х		х	х
Timed up and go test	Х				Х		Х	Х
Rosenberg view x-ray	Х				Х^		Х^	Х^
Weight bearing AP/Lateral view x-rays	X°		Х	Х^				
Participant completed questionnaires (KOOS, OKS, EQ5D-3L, Pain VAS, Health Resource Use)	х	X*			х	х	х	х
Randomisation	Х							
Surgery (KR or KJD)		Х						
Surgical details		Х		Х^				
Distraction of external fixator (KJD only)		Х^	Х^					
Removal of external fixator (KJD only)				Х^				
Complications		Х	Х	Х^	Х	Х	Х	Х
Additional knee related surgery		х	х	Х^	Х	Х	Х	Х
Concomitant medications	Х	Х	Х	Х^	Х	Х	Х	Х

° If not performed within last 6 months prior to baseline

OKS: Oxford Knee Score

* KOOS only, up to 1 day before surgery

^ KJD arm only

KOOS: Knee Injury and Osteoarthritis Outcome Score

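### Range of movement and timed-up-and-go have no planned between-arm estimate with an interval, and the range-of-movement formula gives the score the wrong sign

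*Protocol*

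**What the plan says.** Section 6.2 lists "Objective assessment of knee function" as the second secondary objective. Section 11.2 gives it two measures, active range of movement and the timed-up-and-go test.

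- **Timing.** Section 11.2 has range of movement "Measured using a goniometer at 3, 12 and 24 months". In the Section 12.2 schedule, the rows "Range of movement using goniometer" and "Timed up and go test" are marked at baseline and months 3, 12 and 24. Those visits apply to all participants, and neither row carries the KJD-only symbol. Section 9.4.1 adds: "The range of movement and timed up and go tests should be performed and all baseline questionnaires completed BEFORE the participant is randomised". Section 9.4.2 requires confirmation that both tests are complete before a participant can be randomised.
- **Analysis.** Section 14.1: "Range of motion and timed up and go functional assessments will be reported descriptively". No between-arm contrast is named. In the same section, the patient-reported measures are compared between arms by standardised area under the curve, and joint survival by a hazard ratio.
- **Definition.** Section 11.2 defines range of movement as the difference between two angles, "extension minus flexion", and adds: "A flexion deformity will be measured as a positive value and hyperextension will be recorded as negative value".

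**The concern.** The trial is open-label and its primary outcome is self-reported pain. Range of movement and timed-up-and-go are the only functional outcomes that do not come from a questionnaire. Loss of motion is also a foreseeable question for this intervention: the frame bridges the knee for six weeks (Section 5.1), a manipulation is attempted at its removal (Section 10.4.3), and stiffness needing manipulation is a listed expected complication (Section 13.2.2).

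With separate summaries by arm and no contrast, a reader cannot readily tell whether function is similar in the two arms or whether the data are too imprecise to say. The baseline values, which must be collected before anyone is randomised, would not be used to sharpen a comparison.

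The formula is a separate matter. A range score with the wrong sign, if programmed as written, reverses the direction of any summary or difference built on it.

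**Working it through.** **1. The plan's own sample size.** Inputs from Section 14.2: margin 8, SD 21, one-sided 2.5%, power 90%, 15% dropout.

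- n per arm = 2 × (1.96 + 1.2816)² × 21² / 8² = 144.8, rounded up to 145. The protocol states 146, so it reproduces to within one patient.
- 146 / 0.85 = 171.8, rounded up to 172 per arm and 344 in total, as stated.

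Nothing in this point affects the sample size. It only borrows the 146 as a planning number.

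**2. Precision of a between-arm difference.** In SD units, the 95% half-width is 1.96 × √[(2/n) × (1 − r²)], where r is the correlation between baseline and follow-up. The protocol gives no r, so a range is assumed. With n = 146 per arm:

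| r (assumed) | Half-width (SD) |
|---|---|
| 0 (unadjusted) | 0.229 |
| 0.3 | 0.219 |
| 0.5 | 0.199 |
| 0.7 | 0.164 |

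The protocol gives no SD for either test. Under assumed SDs, the unadjusted half-widths (0.229 × SD) are:

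- Range of movement, SD 10, 15 or 20 degrees: 2.3, 3.4 or 4.6 degrees.
- Timed-up-and-go, SD 2, 3 or 5 seconds: 0.46, 0.69 or 1.15 seconds.

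**3. Which secondary outcomes get a contrast (Section 14.1).**

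| Outcome | Arms measured | Planned contrast |
|---|---|---|
| Patient-reported measures | Both | Area under the curve |
| Joint survival | Both | Hazard ratio |
| Joint space width | KJD only | None possible |
| Range of movement, timed-up-and-go | Both | None |

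Joint space width is also descriptive, but it is measured in one arm only. That reason does not apply to the two functional tests.

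**4. Sign of the range score.** Apply the formula under the stated convention. The angles are illustrative; a 10-degree deformity is the largest that Section 8.3.1 admits.

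| Extension | Flexion | As written | Flexion minus extension |
|---|---|---|---|
| +10 | 120 | −110 | 110 |
| +5 | 110 | −105 | 105 |
| 0 | 120 | −120 | 120 |
| −5 | 130 | −135 | 135 |

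Every range is negative, and the knee with the widest arc has the lowest score. Suppose the KJD mean range were 105 degrees and the KR mean 110. As written, KJD minus KR is −105 − (−110) = +5, which looks like a gain for KJD. With flexion minus extension it is 105 − 110 = −5, the 5-degree deficit that it is. The size is unchanged; only the direction flips.

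**The case against.** The strongest reply is that descriptive reporting is a deliberate and coherent choice. Section 6.2 commits only to examining and reporting, Section 14.2 says that secondary outcomes carry no power, and Section 14.1 then plans a descriptive report. These statements agree. This stands: there is no contradiction, and a reader who infers that the second secondary objective goes unanswered is holding it to a standard that it does not set. It is answered descriptively. The lead-in to the objectives does not by itself account for the choice, however, since the same lead-in covers objectives whose outcomes are compared between arms.

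A reader might also infer that these tests will be reported with no measure of uncertainty at all. The protocol does not say that. A descriptive report can include SDs or confidence intervals by arm, and the SAP, which is not shown, may set this out. What is absent from the protocol is a planned contrast between arms. Lack of power argues against tests and claims, but not against giving an estimate with an interval.

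Two stronger readings also fail:

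- Function is not left without any comparison. The KOOS daily-living and sport domains and the Oxford Knee Score are compared through the patient-reported analysis.
- The two tests are not a bias-free check on the questionnaires. Section 7.1 blinds neither participants nor staff, both tests depend on participant effort, and no blinded assessor is named for them.

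On the formula, the reply is that both angles are recorded, the magnitude is clear from the wording, and the same rule applies to both arms. This is correct, and it is why the error is minor. The sign as written is still wrong.

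**Conclusion.** The point holds as a minor one, in two parts.

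**Analysis.** The protocol plans no between-arm estimate with uncertainty for its only functional outcomes that are not self-reported, although the data for one are collected in both arms from baseline to month 24. This is a missed improvement at almost no cost, not a mistake. Precision is no reason to leave it out: the half-width is about 0.23 SD unadjusted, and 0.20 to 0.16 SD for assumed baseline correlations of 0.5 to 0.7. These figures rest on 146 evaluable per arm, which is the KOOS pain number at 12 months. Month 24 may be less precise, and the per-protocol population, which Section 14.1 makes primary, may be of a different size. Results in degrees or seconds depend on SDs that the protocol does not give.

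**Definition.** The range-of-movement formula is wrong as written under the protocol's own sign convention. It loses no data and changes no magnitude, but it reverses the direction of the score.

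**What to change.** 1. In Section 14.1, keep the descriptive summaries. Add the KJD minus KR mean difference with 95% confidence interval for each test at months 3, 12 and 24, adjusted for the baseline value, delivery unit and OA severity. State that it is an estimate only, with no test and no power claim. If timed-up-and-go is skewed, analyse log time. State the direction of benefit for each, since a longer time is worse and a wider range is better.
2. In Section 11.2, define range of movement as flexion angle minus extension angle, and keep the stated sign convention for deformity and hyperextension.
3. When reporting, note that participants and assessors were not blinded.

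The cost is a few lines of analysis and one corrected phrase. No new data, visits or change to the sample size are needed.
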